6.2.3 Suspected Unexpected Serious Adverse Reaction

6.2.3.1 Definition of Suspected Unexpected Serious Adverse Reaction

A suspected unexpected serious adverse reaction (SUSAR) is an SAE for which there is a reasonable possibility that the drug caused the SAE and is considered unexpected per the current Reference Safety Information (RSI). For the purposes of expedited safety reporting, “reasonable possibility” means there is evidence to suggest a causal relationship between the drug and the AE.

An AE is considered “unexpected” for regulatory reporting purposes if it is not listed in the current RSI within the Investigator’s Brochure or is not listed at the specificity or severity that has been observed.

6.2.3.2 Suspected Unexpected Serious Adverse Reaction Expedited Reporting Requirements

The Sponsor or its designee will submit SUSARs to appropriate Regulatory Authorities (including Competent Authorities in all Member States concerned), IRBs/ECs, and Investigators as per local laws and regulations. Fatal and life-threatening SUSARs will be submitted no later than 7 calendar days of first knowledge of the event and follow-up information submitted within an additional 8 days. All other SUSARs will be submitted within 15 calendar days of first knowledge of the event.

The Investigator will notify the IRBs/ECs of SUSARs in accordance with IRB/EC requirements and local laws and regulations. A copy of this notification must be provided to the Sponsor and/or its designee.

6.2.3.3 Urgent Safety Measures and Non-Suspected Unexpected Serious Adverse Reaction Reporting

An urgent safety measure (USM) is an intervention that is not defined by the protocol and can be put in place with immediate effect without needing to gain prior approval by the Sponsor, relevant competent authorities, IRB/EC, where applicable, in order to protect subjects from any immediate hazard to their health and/or safety. Either the Investigator or the Sponsor can initiate a USM. The cause of a USM can be safety-, product-, or procedure-related.

Investigators are required to report any USMs to the Sponsor or its designee **within 24 hours**. The Sponsor or its designee will inform the Regulatory Authorities, IRBs/ECs, and other Investigators of any events that may occur during the clinical study that do not fall within the definition of a SUSAR, but may affect the safety of subjects participating in the clinical study, as required, in accordance with applicable laws and regulations. The reporting collection period for

urgent safety issues is the period from the signing of the ICF until the Year 10 Visit or the subject withdraws from the study.

The Investigator will notify the IRB/ECs of USMs in accordance with IRB/EC requirements and local laws and regulations. A copy of this notification must be provided to the Sponsor and/or its designee.

Non-SUSARs will be maintained by the Sponsor and provided in annual safety reports and/or other aggregate periodic summary reports to Regulatory Authorities and IRB/ECs as per local laws and regulations.

6.3 Adverse Event and Serious Adverse Event Severity Grades and Relationship to Investigational Medicinal Product

6.3.1 Assessment of Severity

The seriousness of an AE should not be confused with its severity. Severity is a measure of intensity (eg, Grades 1 through 5 or mild, moderate, and severe), whereas seriousness is based on subject/event outcome as defined by the criteria in [Section 6.2](#). The Investigator is responsible for assessing the severity of an AE according to the NCI CTCAE version 4.03 ([Appendix 6](#)).

It is important to distinguish between seriousness (AE versus SAE) and severity (Grades 1 to 5) of AEs. Seriousness, not severity, serves as a guide for defining regulatory reporting obligations.

An AE of severe intensity need not necessarily be considered serious. For example, nausea that persists for several hours may be considered Grade 3 nausea, but not an SAE. On the other hand, a stroke that results in only a limited degree of disability may be considered a Grade 1 stroke, but would be a SAE.

Many common AEs are able to be graded according to NCI-CTCAE criteria. AEs that do not have a corresponding NCI-CTCAE term will be assessed according to the general guidelines for grading used in the NCI-CTCAE version 4.03 as shown in [Table 4](#).

Table 4: Adverse Event Severity Grading Scale (NCI-CTCAE)

Grade	Description
1	Mild: asymptomatic or mild symptoms; clinical or diagnostic observations only; intervention not indicated
2	Moderate: minimal, local or noninvasive intervention indicated; limiting age-appropriate instrumental activities of daily living (ADL) ^a
3	Severe or medically significant but not immediately life-threatening: hospitalization or prolongation of hospitalization indicated; disabling; limiting self-care ADL ^b
4	Life threatening consequences; urgent intervention indicated
5	Death related to AE

ADL = activities of daily living; AE = adverse event; NCI-CTCAE = National Cancer Institute Common Terminology Criteria for AEs.

^a Instrumental ADL refer to the following examples: preparing meals, shopping for groceries or clothes, using the telephone, managing money.

^b Self-care ADL refer to the following examples: bathing, dressing and undressing, feeding oneself, using the toilet, taking medications, not bedridden.

Source: [Appendix 6](#).

Any Grade 3 and 4 clinical laboratory result that represents an increase in severity from baseline will be reported as an AE if it is not associated with a diagnosis already reported on the eCRF. A Grade 1 or 2 clinical laboratory abnormality should be reported as an AE only if it is considered clinically significant by the Investigator.

6.3.2 Assessment of Relationship

The Investigator is responsible for assessing whether the event was related to IMP based on the guidelines in [Table 5](#).

Table 5: Assessment of Relatedness

Not related to IMP	Another cause of the event is most plausible; and/or clinically plausible temporal sequence is inconsistent with the onset of the event and the IMP; and/or a causal relationship is considered biologically implausible.
Possibly related to IMP	An event that follows a reasonable temporal sequence with the IMP, but that could readily have been produced by a number of other factors.
Related to IMP	An event that follows a reasonable temporal sequence with the IMP, and the event could not be reasonably explained by the known characteristics of the subject's clinical state.

IMP = investigational medicinal product.

For the purposes of reporting to regulatory agencies, AEs deemed as possibly or related to IMP will be considered related and those deemed not related will be considered unrelated.

There may be situations in which an SAE has occurred and the Investigator has minimal information to include in the initial report to the Sponsor. While it is very important that the

Investigator always assesses causality for every event before the initial transmission of the SAE data to the Sponsor, the initial report should be submitted without delay (ie, **within 24 hours** of awareness). With limited or insufficient information about the event to make an informed medical judgment and in absence of any indication or evidence to establish a causal relationship, a causality assessment of “no” is to be considered. In such instance, the Investigator is expected to obtain additional information regarding the event as soon as possible and to re-evaluate the causality upon receipt of additional information. The medically qualified Investigator may revise the assessment of causality in light of new information regarding the SAE and shall send an SAE follow-up report in the eCRF and follow-up SAE worksheet with the new information and updated causality assessment.

6.4 Clinical Laboratory Abnormalities and Other Abnormal Assessments as Adverse Events or Serious Adverse Events

The Investigator must review the laboratory report, document this review, and record any clinically significant changes occurring during the study as an AE. The laboratory reports must be filed with the source documents.

Clinical significance of out-of-range laboratory findings is to be determined and documented by the Investigator or Sub-Investigator who is a qualified physician. Abnormal laboratory findings associated with the underlying disease are not considered clinically significant unless judged by the Investigator to be more severe than expected for the subject's condition.

Laboratory abnormalities that are considered to be clinically significant by the Investigator must be recorded as AEs. Laboratory abnormalities (eg, clinical chemistry, hematology, coagulation parameters, and urinalysis) that require medical or surgical intervention must be recorded as an AE, as well as an SAE if the abnormality meets SAE criteria (defined in [Section 6.2.1](#)). In addition, laboratory or other abnormal assessments (eg, ECG, X-rays, vital signs) that are associated with signs and/or symptoms must be recorded as an AE or SAE if they meet the definition of an AE or SAE as described in [Sections 6.1.1](#) and [6.2.1](#), respectively. If the laboratory abnormality is part of a syndrome, record the syndrome or diagnosis (eg, anemia), not the laboratory result (eg, decreased hemoglobin).

The following laboratory abnormalities should be recorded as AEs regardless of whether considered to be clinically significant, unless the abnormality is considered to be part of an integrated diagnosis:

- Troponin I or Troponin T values above the ULN (or a non-zero value if no ULN is reported) for which additional diagnostic workup and/or treatment is indicated per consultation with the site pediatric cardiologist (see [Section 4.6.1](#))
- Platelet values below the lower limit of normal, or below the subject's baseline value if abnormal at baseline

Please contact the Medical Monitor if there are questions regarding how to capture laboratory abnormalities.

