7.6 Study Safety Stopping Rules

Dosing of additional subjects will be paused and the DMC will conduct a review if any of the following stopping criteria are reached:

- One Grade \geq 4 AE or the occurrence of the same treatment-related Grade \geq 3 AE on 2 or more occasions
- Any Grade \geq 3 neuromuscular AE in a treated subject considered possibly related or related to AT132, as assessed by the Investigators
- Any Grade \geq 3 cardiac AE in a treated subject considered possibly related or related to AT132, as assessed by the Investigators
- Any Grade \geq 3 hepatobiliary AE in a treated subject considered possibly related or related to AT132, as assessed by the Investigators

The DMC may advise that the study should be terminated or that clinical protocol should be revised to mitigate the risk to subjects. Such revisions may include changes to the enrollment criteria, changes in the monitoring plan, and/or changes to the informed consent form.

If dosing of additional subjects is paused, all remaining protocol specified study visits, safety assessments, and end-of-study procedures should be completed in subjects who have already been dosed. If any Study Safety Stopping Rules are met while the study is already paused or on hold, these will be reported to the DMC since such criteria may change management of a previously treated subject.

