4.6.1 Adverse Events

Treatment-emergent AEs (TEAEs) are defined as any AEs, regardless of relationship to study drug, that have an onset or worsening in severity on or after the time/date of the baseline (dosing) visit (the reference date).

All descriptive statistics will be presented by dose level and all dose levels combined. Unless otherwise indicated, AE summaries will be presented by the following periods:

- Baseline through Week 24 (inclusive)
- >Week 24 through Week 48
- >Week 48 to End of Study
- Overall for the study

An overview table to report the number and percentage of participants and number of events will include the following:

- TEAEs,
- Drug related TEAEs,
- Serious TEAEs,
- Serious drug related TEAEs,
- TEAEs leading to withdrawal of study
- Drug-related TEAEs leading to withdrawal of study
- TEAEs leading to death,
- Drug related TEAEs leading to death,
- NCI-CTCAE Grade 3 or higher TEAEs
- NCI-CTCAE Grade 3 or higher drug related TEAEs
- Deaths

NCI-CTCAE v4.03 or higher will be used for assessment of grade.

The number and percentage of participants with TEAEs, as classified by SOC and PT will be summarized for each treatment group and overall. Summaries will be provided for the following:

- TEAEs
- Drug related TEAEs,
- Serious TEAEs,
- Drug related serious TEAEs,
- TEAEs leading to withdrawal of study,
- Drug related TEAEs leading to withdrawal of study,
- NCI-CTCAE Grade 3 or higher TEAEs,
- NCI-CTCAE Grade 3 or higher drug-related TEAEs,
- TEAEs leading to death,
- Drug-related TEAEs leading to death,
- Frequently reported ($\geq 10\%$ in All Dosed Group) TEAEs by preferred term,
- Frequently reported ($\geq 5\%$ in Any Treatment Group) TEAEs Excluding Serious TEAEs (this table will only be presented for the overall study duration)

Related AEs are those with relationship to study medication reported as “possible” or “related”. If relationship to study drug of an AE reported by treated participants is not recorded, the relationship will be imputed as “possibly related”, for analysis purposes. In the participant listing, both collected and imputed values will be presented.

An overview table to report number of events, and events adjusted by participant year from date of drug exposure (each summary classified by category below, SOC and PT) will include the following:

- Serious respiratory TEAEs,
- Serious non-respiratory TEAEs

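### Protocol 6.3.2 invites a 'no' on causality for an initial SAE report with too little information, which Table 5 does not support; if nothing further arrives, the event stays classed as unrelated

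*Protocol*

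**What the plan says.** Protocol 6.3.2 asks the investigator to rate each event by Table 5, which has three categories.

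- 'Not related' needs a stated reason: "Another cause of the event is most plausible; and/or clinically plausible temporal sequence is inconsistent with the onset of the event and the IMP", or a causal relationship judged biologically implausible.
- 'Possibly related' is "An event that follows a reasonable temporal sequence with the IMP, but that could readily have been produced by a number of other factors".
- 'Related' needs reasonable timing and no reasonable explanation in the subject's known clinical state.

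For regulatory purposes, "AEs deemed as possibly or related to IMP will be considered related and those deemed not related will be considered unrelated".

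The same section then covers the initial SAE report, due within 24 hours, when the investigator has little to go on. With limited or insufficient information, and "in absence of any indication or evidence to establish a causal relationship", it says that "a causality assessment of “no” is to be considered". The investigator is expected to seek more information as soon as possible and reassess when it comes, and may revise the rating in a follow-up report.

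SAP 4.6.1 counts an AE as related when the rating is 'possible' or 'related'. "If relationship to study drug of an AE reported by treated participants is not recorded", it is imputed as possibly related for analysis.

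**The concern.** The sentence turns an absence of information into a negative rating, which the table above it does not permit. It also runs against the SAP: a blank field counts as related, while a 'no' entered for want of information counts as unrelated.

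The rating feeds three later steps.

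- **Expedited reporting.** A SUSAR requires that "there is a reasonable possibility that the drug caused the SAE" (Protocol 6.2.3.1), and 6.3.2 carries a 'not related' rating straight into unrelated status for regulators.
- **Safety criteria in Protocol 7.6.** The hepatobiliary criterion applies to a Grade 3 or higher "hepatobiliary AE in a treated subject considered possibly related or related to AT132, as assessed by the Investigators". The neuromuscular and cardiac criteria have the same condition, and the repeated Grade 3 or higher criterion counts treatment-related events only.
- **SAP tables.** Drug-related, drug-related serious and drug-related fatal TEAEs, and drug-related AESIs, all use this field.

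The point is still live. Dosing has ended, but 7.6 has criteria met during a pause or hold reported to the DMC, and AE collection continues through a 10-year follow-up. Under Protocol 5.2, visits after Month 60 may be remote, and safety information on children who leave early may come from public data or medical-record requests. Information may be thin in those settings.

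**Working it through.** This is mainly a comparison of texts; arithmetic enters only to show scale.

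**Step 1: when the default applies.** Three things must hold: an initial SAE report with minimal information; information too limited for an informed medical judgement; and no indication or evidence of causality. Even then, 'no' is something to consider, not an automatic entry.

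**Step 2: does such a case meet Table 5 'Not related'?**

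| Table 5 ground for 'Not related' | Met by insufficient information alone? |
|---|---|
| Another cause most plausible | No: this needs knowledge of another cause |
| Timing inconsistent | No: this needs a judgement on timing |
| Biologically implausible | No: this needs knowledge of the event |

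Nor does the case automatically meet 'Possibly related', which needs a reasonable temporal sequence. If the timing is known and reasonable and other causes could readily explain the event, Table 5 gives 'Possibly related'. If even the timing cannot be judged, Table 5 has no category.

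**Step 3: follow each entry downstream.**

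| Entry | Regulatory mapping (6.3.2) | Causality-dependent 7.6 criteria | SAP drug-related tables |
|---|---|---|---|
| 'No' | Unrelated | Not counted | Excluded |
| 'Possibly related' | Related | Counted | Included |
| Not recorded | Not stated | Not stated | Included by imputation |

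A default 'no' is a recorded value, so the SAP imputation never reaches it.

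**Step 4: how long the 'no' lasts.** Reassessment is tied to receipt of additional information. Section 6.3.2 sets no deadline and has no rule for the case where none comes. With new information the effect is a delay; without it, the 'no' is final.

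**Step 5: scale.** Protocol 1.4.2 gives subjects with AT132-related SAEs at the 08 July 2020 cut-off, and the percentages reproduce:

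- low dose: 1/6 = 16.7%
- high dose: 8/17 = 47.1%

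The number of SAEs rated 'no' by default is not given. Assume, for illustration only, that *m* further children per group were re-rated as related:

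| *m* | Low dose, (1 + *m*)/6 | High dose, (8 + *m*)/17 |
|---|---|---|
| 0 | 16.7% | 47.1% |
| 1 | 2/6 = 33.3% | 9/17 = 52.9% |
| 2 | 3/6 = 50.0% | 10/17 = 58.8% |

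Each child is worth 1/6 = 16.7 points or 1/17 = 5.9 points. This shows how sensitive small groups are; it does not estimate an effect of 6.3.2.

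**The case against.** The strongest reply is that the sentence is narrow and well surrounded by safeguards.

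- It concerns a provisional rating in an initial report, has a second condition, and expects reassessment. Hepatobiliary, myocardial, CK and platelet events are listed as identified risks in Protocol 1.5, so an investigator could reasonably see an indication of causality there and never reach the default.
- Every SAE goes to the sponsor within 24 hours whatever its rating, and the signed worksheet must explain the causality assessment (6.2.2). SAEs are followed actively (6.2.2.1), and severe hepatic abnormalities are reported as SAEs (6.5.3.2).
- The DMC also reviews important medical events (7.5), and the single Grade 4 or higher criterion in 7.6 states no relatedness condition.
- The SAP tabulates all TEAEs, serious TEAEs, Grade 3 or higher TEAEs, fatal TEAEs and AESIs regardless of causality.
- The SAP rule concerns a missing field at analysis, a different situation from a provisional judgement.
- Replacing 'no' with a blanket 'possibly related' would also depart from Table 5 where timing is unknown.

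Most of this stands. It limits the reach, and the last item shapes the remedy. None of it alters the recorded rating, which alone sets the regulatory mapping in 6.3.2 and entry to the drug-related tables. The required explanation does not help if lack of information is itself an accepted explanation.

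**Conclusion.** Protocol 6.3.2 is inconsistent with its own Table 5 and leads to the opposite result from SAP 4.6.1. The usual consequence is a delayed related rating. A lasting one arises only where no further information is received or the rating is not revised. It then touches regulatory status, the four causality-dependent criteria in 7.6 (Grade 3 or higher neuromuscular, cardiac or hepatobiliary, and repeated Grade 3 or higher), and the drug-related tables. The size is unknown. The conclusion assumes that some sites use the default as written and that some reports are never completed.

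A reader might infer more, and the documents do not support it:

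- **That related events were missed, or that the 1/6 and 8/17 figures favour the product.** No event is shown to have been defaulted. Those figures predate protocol v8 (16 November 2020), and nothing shows that the sentence was in force then.
- **That a poorly documented death would escape the DMC.** A fatal AE is Grade 5 and meets the Grade 4 or higher criterion.
- **That expedited deadlines were or would be missed.** SUSAR status also depends on unexpectedness against the reference safety information in the Investigator's Brochure, which is not part of these documents.
- **That any SAE with thin information is to be rated unrelated.** The second condition and the expected reassessment rule that out.

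**What to change.** Reconcile 6.3.2 with Table 5 and SAP 4.6.1 by replacing the sentence with a rule to this effect: 'Not related' may be recorded only when a Table 5 'Not related' criterion is met and documented; otherwise record 'possibly related' if the timing is reasonable, or leave causality pending or not recorded, to be handled as possibly related for reporting and under SAP 4.6.1 until updated.

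Two adjustments follow. Section 6.3.2 now expects causality to be assessed before the first transmission, and 8.6.1 does not accept blank eCRF fields unless the instructions allow them, so the eCRF instructions need to permit a pending entry. SAP 4.6.1 should state that pending is treated as not recorded.

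Also check existing SAEs rated 'not related' for a documented Table 5 ground, and query those without one. This would show whether the default was ever used.

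Cost: one protocol sentence, one line in the SAP, an update to the SAE and eCRF completion instructions, and a one-off query. The downside is a few more expedited reports and slightly higher related-event rates, in the conservative direction the SAP already takes.

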6.5 AEs and Laboratory Results of Special Interest

See current AT132 Investigator's Brochure for current RSI.

6.5.1 Cardiac Enzyme Elevations

Troponin elevations have been observed in the ASPIRO study. Elevation of cardiac enzymes (including troponin levels) should be evaluated as described in [Section 4.6.1](#).

6.5.2 Management of Potential Immune Responses

Elevations of hepatic transaminases, CK, and troponin I, likely representing an immune response to the study treatment, have been reported in Study ATX-MTM-002 and are considered identified risks associated with AT132 administration. Refer to the Investigator's Brochure for details.

Guidelines for monitoring and management of such events are provided in [Section 4.6](#). Appropriate care for an individual subject will be determined by the Investigator based on an assessment of the subject's overall medical status. Corticosteroid treatment typically resolves the elevation of liver transaminases. However, when adverse events related to the immune response are of significant concern (eg, rAAV vector dose 1×10^{14} vg/kg and/or a transgene-mediated immune response), immunomodulation may include medications such as rapamycin (sirolimus), mycophenolate mofetil, calcineurin inhibitors (eg, cyclosporine, tacrolimus), and rituximab ([Prasad, 2022](#)).

